CLINICAL STUDY PROTOCOL

C. Kenneth and Dianne Wright
Center for Clinical and Translational Research

SAFEty Study of Early Infusion of Vitamin C for Treatment of Novel Coronavirus Acute Lung Injury

(SAFE EVICT CORONA-ALI)

Protocol Version: 1.83

Protocol Version IRB approved: 08/10/2021

VCU IRB Number: HM20018977

ClinicalTrials.gov Identifier: NCT04344184

IND: 149518

Study Personnel

Principal Investigator(s) [name]
Virginia Commonwealth University
Department of Internal Medicine
Pulmonary and Critical Care Medicine

[name], MD
Virginia Commonwealth University
Department of Internal Medicine
Pulmonary and Critical Care Medicine

Co-Investigators
[name]
Central Virginia VA Health System
Department of Internal Medicine
Gastroenterology and Hepatology Division

[name]
Department of Biostatistics
Virginia Commonwealth University,
Massey Cancer Institute

[name]
Virginia Commonwealth University
Department of Surgery
Division of Trauma Surgery

[name]
Virginia Commonwealth University
Department of Surgery
Division of Trauma Surgery

Clinical Coordinators: [name] and [name]
Virginia Commonwealth University
Department of Internal Medicine
Pulmonary and Critical Care Medicine

Regulatory Contact: [name]
Virginia Commonwealth University
Department of Internal Medicine
Pulmonary and Critical Care Medicine

Synopsis

Study Description

The purpose of this proof-of-concept, phase 2 safety study is to examine the safety profile, and possible therapeutic effects of high-dose, intravenous vitamin C (HDIVC) compared to placebo in hospitalized adult patients with novel Coronavirus COVID-19 and hypoxemia.

Objectives

To assess the safety profile of a 4-day (96-hour) intravenous vitamin C treatment protocol (comprised of four intravenous infusions a day, that is 50 mg/kg every 6 hours) in patients with laboratory-confirmed SARS-CoV-2 infection manifesting COVID-19 (Novel Coronavirus Disease 2019) with hypoxemia. While performing this phase 2 proof-of-concept, safety study, we will explore the following hypotheses:

Endpoint

Primary Endpoint (Safety): HDIVC infusion does not worsen the patients' outcomes, as measured by differences in the mean 9-point (from 0 to 8) World Health Organization (WHO) ordinal scale for disease improvement, between the two populations at 28, 60 and 90 days:

Table 1.

Patient State	Descriptor	Score
Uninfected	No clinical or virologic evidence of infection	0
Ambulatory	No limitation of activities	1

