3.1 Objectives and Endpoints

OBJECTIVES	ENDPOINTS	JUSTIFICATION FOR ENDPOINTS
Primary		
WHO COVID-19 9-point Ordinal Scale Outcome	MEAN SCORE ON DAY 28, 60 AND 90	This ordinal scale captures a range of safety outcomes and is ideal for safety studies. If any other unanticipated clinical harms of high-dose intravenous vitamin C occur, will be captured on this outcome.
Secondary		
Renal safety biomarkers	Daily serum oxalate Daily urinalysis 24-hour urine oxalate on day 5	Measured biomarkers will provide a sensitive way to identify the mechanisms of oxalate nephropathy
AKI-free days at day 28 and 90	Renal-failure free days, with AKI defined by the KDIGO criteria (see table below).	This endpoint aims to identify long-term kidney outcomes among the two groups
All-cause mortality at 28 60 and 90 days	Safety Endpoint	If the therapy offers significant benefit, or harm, compared with placebo
Exploratory biomarkers	Ferritin, D-dimer, LDH, CRP, plasma IL-6 on day 7	The biomarkers aim to help interpret the outcomes, and further explain clinical differences in the above-measured outcomes
Ascorbate trough levels	Plasma ascorbate at baseline (0 hours) levels at 24 hours, 48 hours, 96 hours and 168 hours	The PK of ascorbate is still unknown in the target patient population
Alive and free of significant respiratory failure through 28-days	At 28-days is the patient alive and not in respiratory failure, the principal cause of death by COVID-19	Respiratory failure defined as at least one of the following: 
 • Endotracheal intubation and mechanical ventilation • •Oxygen delivered by high-flow nasal

		
cannula (heated, humidified)
 
 • Oxygen delivered via reinforced nasal cannula at flow rates >20L/min with fraction of delivered oxygen ≥ 0.5) • Noninvasive positive pressure ventilation (CPAP or BIPAP) • Extracorporeal membrane oxygenation (ECMO of any type)

Alive and free of mechanical ventilation at 28-days
	
Proportion of patients alive and free of invasive mechanical ventilation at 28-days.
	
Is the patient dependent on mechanical ventilation by 28-days, that is development of significant chronic respiratory failure

WHO COVID-19, 9-point Ordinal Outcome Scale		
Patient State	Descriptor	Score
Uninfected	No clinical or virologic evidence of infection	0
Ambulatory	No limitation of activities	1
	Limitation of Activities	2
Hospitalized mild disease	Hospitalized, no oxygen therapy	3

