4.4 End of Study Definition

Active treatment period will continue for 4 days, that is 16 infusions of 50 mg/kg intravenous vitamin C, 30-minutes each infusion. The last study-specific bloodwork will be collected at 7 days. **All patients will remain in the study through the end of double-blind period and final study blood collection.** Participation will end if patient withdraws the consent or is lost to follow-up. Clinical data, including a final blood draw, will be collected through day 7. All subjects will be followed to day 28 via chart review for collection of clinical outcomes data. 90-day secondary outcomes will be assessed either during clinic visits or via telephone at 60 and 90 days. **Only acceptable reasons for early study termination include consent withdrawal, or loss to follow-up.**

5 - Study Population

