8.3.6 Adverse Events, Serious Adverse Events, and Unanticipated Problems

Adverse events (AEs), serious adverse events (SAEs), and unanticipated problems (UPs) occurring at VCU will be managed and reported in accordance with [VCU/VCUHS Clinical Research Standard Operating Procedures #CR-RE-300.1: Adverse Event Management and Reporting](#). Those occurring at the VA will be managed and reported in accordance with the VA's standard operating procedures.

All serious adverse events (SAEs) will be followed until a satisfactory resolution or until the site investigator deems the event to be chronic or the participant is stable.

The PI/sponsor will be responsible for notifying the Food and Drug Administration (FDA) of any unexpected fatal or life-threatening suspected adverse reaction as soon as possible, but in no case later than 7 calendar days after being informed about the event. In addition, the PI/sponsor must notify FDA and all participating investigators in an Investigational New Drug (IND) safety report of potentially serious risks, from clinical trials or any other source, as soon as possible, but in no case later than 15 calendar days after the PI/sponsor determines that the information qualifies for reporting.

[figure not shown]
9 - Statistical Considerations

[figure not shown]
[figure not shown]
Model Set-Up:

We plan to use a two-sample, unequal-variance 2-tail t-test for comparing the mean differences between the two groups, the vitamin C arm and placebo arm. The actual interventions will be blinded and will be revealed after the completion of statistical analysis, therefore, we will be labeled as group A and group B. No one besides the DSMB and independent statistician supporting the DSMB will have access to the comparative data, even if the treatment groups are masked as group A and Group B.

[figure not shown]
This is a proof-of-concept study, **with predetermined sample sizes** for each arm, which is 30 patients for group A and 30 patients for group B, therefore the **power analysis is driven by the predetermined sample size and did not determine the sample size.**

[figure not shown]

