Therefore, this proof-of-concept study of 60 patients, 30 allocated to the treatment arm and 30 to the placebo arm, will have 96% power (1-beta (β)) to detect an **average of 1-point difference** in the primary outcome, the WHO COVID-19 ordinal scale, with an alpha error probability (α) of 4% (0.04). This is by applying a two-tail, t-test with unequal variances (see figure below).

[figure not shown]

For binary secondary outcomes, we plan to use the chi-squared test, with 1-degree of freedom. The expected effect size for an alpha level of 0.05 and power of 80% is 0.36, as shown in the figure below.

In contrast, for a constant hypothetical effect size of 0.2, a phase 3 trial will require at least 200 patients to achieve a power of 80% and an alpha of 0.05 (yellow line, figure below).

Planned Interim Analyses:

No planned interim analyses will be conducted in this study. The results will be analyzed after the 60th patient has finished enrollment and has been discharged from the hospital (phase 1). There are no provisions to stop the trial early for efficacy.

Missing Data

The primary outcome, the WHO-COVID-19 scale is encompassing missing data from death or hospital discharge. Missing laboratory or clinical data due to patient death, or discharge will not be imputed given this practice will introduce systematic bias, since they are not missing at-random. For organ-system data, the highest scores will be attributed after patient death, since death causes cessation of all organ function, and any imputation method will underestimate the severity. For missing-at-random data, multiple imputation with a pattern-mixture model with control-based pattern imputation will be used, with 50 imputed data sets, in order to compensate for data that may be missing at random.

10 - Supporting Documentation and Operational Considerations

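### The stated 96% power for a 1-point difference needs a WHO score SD of about 1.0, which is implausible for ICU patients; at SDs of 1.5 to 3.0 power is 68% to 22%

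*Combined protocol and SAP*

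**What the plan says.** The Synopsis words the primary endpoint as a safety claim, "Primary Endpoint (Safety): HDIVC infusion does not worsen the" patients' outcomes, measured by the difference in mean score on the 9-point WHO scale (0 to 8, death = 8). Section 3.1 gives the endpoint as "MEAN SCORE ON DAY 28, 60 AND 90". Section 9 sets the test: "We plan to use a two-sample, unequal-variance 2-tail t-test for comparing the mean differences between the two groups".

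On power, Section 9 says: "Therefore, this proof-of-concept study of 60 patients, 30 allocated to the treatment arm and 30 to the placebo arm, will have 96% power" for an average difference of 1 point "in the primary outcome, the WHO COVID-19 ordinal scale, with an alpha error probability (α) of 4% (0.04"). It adds: "This is by applying a two-tail, t-test with unequal variances (see figure below"). The figures are not reproduced in the copy reviewed, and the readable text gives no SD. Section 9 also says that the "power analysis is driven by the predetermined sample size and did not determine the sample size".

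Entry requires ICU level of care (Sections 5.1 and 5.2). Section 6.3 stratifies on WHO 3-5 versus 6-7 at enrolment. The schedule in Section 8.1.1 includes WHO scoring at days 60 and 90.

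**The concern.** A power figure for a difference in means depends on the SD. The plan states 96% without condition, so it implies an SD, and that value can be solved for and compared with the endpoint. By day 28, and more so by days 60 and 90, a score of this kind tends to split: deaths sit at 8 and recovered patients at 0 to 2. Even a few deaths then produce a large SD.

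The trial's main claim is that the infusion does not worsen outcomes, yet the planned test is a two-sided test of difference. The readable text gives no decision rule for that claim. A non-significant result could therefore be taken as support for safety, and a reader who believes the 96% would conclude that a 1-point harm had almost been ruled out. This reading is an inference from the wording; the plan does not state it.

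**Working it through.** **Inputs.** From Section 9: n = 30 per arm, difference 1 point, two-sided alpha 0.04, t-test. The SD is not in the readable text, so it is solved for first and then varied as an assumption. With equal SDs and equal arms, the Welch test and the ordinary t-test have practically the same power, so df = 58 is used.

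**1. Reproduce the plan's figure.** The noncentrality is 1/(SD × √(2/30)), with √(2/30) = 0.2582, and the critical value is t(0.98, 58) = 2.101. At SD 1.0 the noncentrality is 3.873 and power is 95.98%. The SD giving exactly 96% is 0.999. Any power that rounds to 96% needs an SD between 0.98 and 1.01. If the SDs differ between arms, their root mean square must still be about 1.0.

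**2. Vary the SD (assumed values).**

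| SD | Power, alpha 0.04 | Power, alpha 0.05 | Difference detectable with 80% power (alpha 0.04) | Expected 96% CI half-width |
|---|---|---|---|---|
| 1.0 | 96% | 97% | 0.76 | 0.54 |
| 1.5 | 68% | 72% | 1.14 | 0.81 |
| 2.0 | 44% | 48% | 1.52 | 1.08 |
| 2.5 | 30% | 33% | 1.90 | 1.36 |
| 3.0 | 22% | 25% | 2.28 | 1.63 |
| 3.5 | 17% | 19% | 2.67 | 1.90 |

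The detectable difference is 0.7615 × SD. The half-width is 2.101 × SD × 0.2582. Power drops below 80% once the SD exceeds 1.31 and below 50% once it exceeds 1.85. The largest possible SD on a 0-8 scale is about 4, so 3.5 is near the extreme. A simulation of the Welch test on normal data (200,000 runs) gave 0.960, 0.685, 0.440 and 0.216 at SD 1, 1.5, 2 and 3.

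**3. What an SD of 1.0 requires.** If a share p has died (score 8) and survivors average m, then SD ≥ √(p(1−p)) × (8−m), with equality only when all survivors have the same score. Setting this to 1.0 gives the highest mortality compatible with the plan's figure:

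| Survivor mean m | Highest mortality for SD 1.0 |
|---|---|
| 1 | 2.1% |
| 2 | 2.9% |
| 3 | 4.2% |
| 4 | 6.7% |
| 5 | 12.7% |

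At m of 6 or more there is no such limit, but those survivors would still be ventilated. With all survivors at 2, the pooled SD is 6 × √(p(1−p)). One death in 60 gives 0.77, two give 1.08, three give 1.31 and six give 1.80.

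**4. Low-mortality illustration (assumed: survivors have mean 2 and SD 1).** SD = √(36p(1−p) + (1−p)). At p = 5% the SD is 1.63 and power about 61%. At p = 10% they are 2.03 and about 43%. These powers apply a normal-data formula to a two-part distribution and are approximate.

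**5. Illustration from the mortality rates in Section 2.2.** The sponsor's earlier ARDS trial had 28-day mortality of 29.8% versus 46.3%. An SD of 1.0 at those rates would need survivors averaging 8 − 1/√(0.298 × 0.702) = 5.81 and 8 − 1/√(0.463 × 0.537) = 5.99, with no spread among them. If instead all survivors score 2 (assumed), the difference in means is (0.463 − 0.298) × 6 = 0.99 points, almost exactly the plan's target. The Welch test's power, by enumerating both binomial death counts with 30 per arm at alpha 0.04, is 25%.

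**The case against.** - **The figures cannot be seen.** They may print the SD, treat the effect as standardised, or already show power over a range. That is so, and the SD cannot be called missing from the plan. But the text states 96% for a 1-point difference without condition, and no figure can change the SD which that implies.
- **The sample size does not rest on the power figure.** Section 9 says so. This stands: the fault is in the stated power and how a null result would be read, not in n.
- **The ARDS trial is a different population.** Section 2.1 aims to treat before ARDS, and Section 5.5 describes non-intubated recruits, although Section 6.3 provides a stratum for WHO 6-7. Mortality may well be lower here. The ceilings in step 3 do not use that trial.
- **The plan already guards against low power.** Section 4.1 has the DSMB review serious adverse events qualitatively for that reason, Section 10.1.5 proposes monthly reviews, and mortality and renal outcomes are separate safety endpoints. This reduces the consequences, but it does not govern interpretation of the primary t-test.
- **The illustrations depend on the model.** Power in step 4 would differ according to whether treatment shifts deaths or survivors' scores, and step 5 assumes both mortality and survivor scores. They show scale only.
- **No passage says a null result will be declared proof of safety.** Correct; that risk is inferred.

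**Conclusion.** The concern holds. The arithmetic behind 96% is right for an SD of 1.0 and for practically no other value. On this scale, in ICU-level patients, that SD needs either very low mortality with tightly grouped survivors (2.9% or less if survivors average 2) or survivors who mostly remain severely ill. It is implausible, not impossible. At SDs of 1.5 to 3.0, which are assumptions, power for a 1-point difference is 68% down to 22%, so the test would miss such a difference in about 32% to 78% of trials. Moving to alpha 0.05 does not change the conclusion. The SD-based power figures treat the score as roughly normal, as the plan's t-test calculation does, and allow for no dropout.

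**What to change.** Keep 60 patients. In Section 9, replace the 96% sentence with power conditional on the SD, and state and justify the SD expected at days 28, 60 and 90. If it is in a figure, move it into the text. Suggested wording:

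> The sample size is fixed at 30 per arm and was not set by a power calculation. Power for a 1-point difference in mean WHO score depends on the SD, which is assumed. At two-sided alpha 0.04 it is 96% for SD 1.0, 68% for 1.5, 44% for 2.0, 30% for 2.5, 22% for 3.0 and 17% for 3.5. The difference detectable with 80% power is about 1.1 to 2.7 points for SD 1.5 to 3.5. The mean difference will be reported with a 96% confidence interval, matching the stated alpha (expected half-width about 0.8 to 1.9 points for the same SDs). A non-significant result alone will not be taken as evidence of no harm.

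No non-inferiority margin is introduced. The cost is a change of wording and a less favourable power statement. No patients, visits or data are added.

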Adult hospitalized patients who have central laboratory-confirmed COVID-19 (Novel Coronavirus Disease-2019, based on a positive SARS-CoV-2 RT-PCR confirmed within 72 hours before enrollment) and new-onset hypoxemia, defined as oxygen saturation (SpO₂) < 93% on pulse oximeter (WHO COVID-19 ordinal scale 3), or requiring any amount of supplemental oxygen (WHO COVID-19 ordinal scale 4-7) at (1) Virginia Commonwealth University Medical Center, and (2) Central Virginia Veterans Affairs (VA) Health System, Richmond, Virginia

Accrual Ceiling

The accrual ceiling for this safety trial is a total of 60 patients, between the two centers.

Phase

Phase 2, proof-of-concept safety trial.

Description of Sites/Facilities Enrolling Participants

The study will involve 2 enrollment sites: (1) Virginia Commonwealth University Medical Center, and the (2) Central Virginia Veterans Affairs (VA) Health System, Richmond, Virginia.

Description of Study Intervention

1. A two-center, prospective, randomized, **double-blind**, placebo-controlled proof-of-concept safety study.
2. A maximum of 60 patients (30 in the treatment, and 30 in the placebo arm) will be enrolled between the two centers.
3. Participants will be randomized to receive either intravenous vitamin C infusion (mixed in 5% dextrose in water) or placebo infusion (5% dextrose in water) in a 1:1 manner.
4. All study drug doses will be administered via an intravenous central or peripheral line infusion. Should no central or peripheral line be available at the scheduled time of infusion, a call should be placed to the pharmacy to determine if the study drug may be co-infused into the line that is infusing a different drug. If co-infusion of study drug is contraindicated, then a maximum of 8 hours may delay study drug infusion. If clinical drug administration schedule is such that study drug will not have an available administration time beyond this delay, a dedicated new intravenous line (peripheral) should be inserted if the patient is agreeable.
5. The study drug will be double-blinded with an identical appearing placebo.
6. Active treatment duration will continue for 96 hours, or until study withdrawal.

[figure not shown]
Study Duration

[figure not shown]
The study will be completed in two phases: Phase 1 will end on day 28, and phase 2 at 90 day follow up.

Participant Duration

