4.1 Overall Design

1. A phase 2, two-center, prospective, randomized, double blind placebo-controlled safety clinical trial.
2. A maximum of 60 patients will be enrolled.
3. Participants will be randomized to receive either intravenous Vitamin C (mixed in 5% dextrose in water) or placebo (5% dextrose in water) in a 1:1 manner.
4. Active treatment will continue for 96-hour period or consent withdrawal or loss to follow-up. One-fourth of the 24-hour calculated dosage will be administered **in 30-minute intravenous infusions of 50 mg/kg and occur every 6 hours** for a total of sixteen 30-minute infusions. **That is 200 mg/kg total per day for 4 days.** The standard of care therapy will be followed. All COVID-19 known therapies will be allowed.
5. All participants will be followed for a total of 28 days on the first phase of the trial and at 60 and 90 days on the second phase.
6. All participants, without exception, will receive the standard of care for COVID-19 including the use of remdesivir, dexamethasone, plasma and other, as a component of standard of care for patients hospitalized with severe disease, in settings where remdesivir is available via the emergency use authorization mechanism.

Analysis/Interim Monitoring:

1. **Only reasons for study withdrawal are withdrawal of consent and, or loss to follow-up**
2. The DSMB will review all SAEs in a narrative and qualitative fashion (not only quantitative), to avoid underpowered statistical misconceptions.
3. Protocol compliance will be monitored by the study team daily discussion. This will take place via investigator conference call and will address challenges encountered. Trial progress will be monitored by an independent Data and Safety Monitoring Board (DSMB) to determine if the study should stop for safety reasons.

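### Section 9's only analysis trigger, discharge of the 60th patient, is not tied to the day 28, 60 and 90 primary endpoint, and no text expressly keeps the blind until day-90 assessments are complete

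*Combined protocol and SAP*

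**What the plan says.** **Endpoint.** The synopsis compares mean scores on the 9-point WHO scale "between the two populations at 28, 60 and 90 days". Section 3.1 repeats this for the primary objective: "MEAN SCORE ON DAY 28, 60 AND 90".

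**Analysis time.** Section 9, under Planned Interim Analyses, says: "The results will be analyzed after the 60th patient has finished enrollment and has been discharged from the hospital (phase 1"). The same paragraph states that no interim analysis is planned. The documents give no other analysis time and no database lock.

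**Phases.** The synopsis (Study Duration) says: "Phase 1 will end on day 28, and phase 2 at 90 day follow up". Section 4.1 agrees that participants are "followed for a total of 28 days on the first phase of the trial and at 60 and 90 days on the second phase".

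**Unblinding.** Section 9, Model Set-Up: "The actual interventions will be blinded and will be revealed after the completion of statistical analysis". The text that follows limits comparative data, even masked as groups A and B, to the DSMB and its independent statistician. Section 10.1.5 repeats that limit, and section 6.3 gives only the study pharmacist access to the randomization repository. None of these restrictions carries an end date.

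**Late follow-up.** Under section 4.4, day-60 and day-90 outcomes are obtained at a clinic visit or by telephone. The same section says: "All patients will remain in the study through the end of double-blind period and final study blood collection".

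**Missing data.** Section 9 covers death, discharge and data missing at random. It does not mention assessments that have not yet fallen due.

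**The concern.** Discharge is a clinical event that can fall on any day after enrollment, while the primary endpoint is fixed at three study days. If the rule is followed as written, the analysis of the trial's results takes place while some primary scores are still in the future. The plan does not say whether they would be left out, imputed or analyzed later. The phase 1 label does not settle this, because the synopsis ends phase 1 on day 28, which need not be the day of discharge.

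The second issue is the blind. The arms are to be revealed after the statistical analysis, and the only analysis with a stated time is the discharge-triggered one. After discharge, the WHO score depends partly on whether activities are limited (score 1 versus 2), established by telephone or in clinic. Knowing the allocation could influence that distinction. Once codes are opened, the loss of blinding cannot be repaired. A plan for a double-blind safety trial should therefore state how long the blind lasts.

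**Working it through.** **1. The plan's own figure.** The plan gives no figure on timing. The nearest is its 96% power for a 1-point difference with 30 per arm and two-sided alpha 0.04. The SD is not in the readable text, so I assume SD = 1 and equal variances. The noncentrality is 1/√(1/30 + 1/30) = 3.87 on 58 degrees of freedom, which gives power 0.960. The figure reproduces, and it counts a score from every one of the 60 patients.

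**2. Trigger against endpoint days.** Let L be the number of days from enrollment to discharge for the 60th patient. At the trigger, that patient's day-28, day-60 and day-90 scores lie 28 − L, 60 − L and 90 − L days ahead. For L = 10 these are 18, 50 and 80 days. For L = 28 they are 0, 32 and 62 days.

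**3. Patients still owing a score.** With steady accrual of r patients per month and a 30.4-day month, the number owing the day-k score at the trigger is about r × (k − L)/30.4, or zero if L is at least k. The documents give neither r nor L, so both are assumptions.

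| r per month | Day 28, L = 10 | Day 60, L = 10 | Day 90, L = 10 | Day 28, L = 28 | Day 60, L = 28 | Day 90, L = 28 |
|---|---|---|---|---|---|---|
| 2 | 1.2 | 3.3 | 5.3 | 0 | 2.1 | 4.1 |
| 4 | 2.4 | 6.6 | 10.5 | 0 | 4.2 | 8.2 |
| 8 | 4.7 | 13.2 | 21.1 | 0 | 8.4 | 16.3 |
| 12 | 7.1 | 19.7 | 31.6 | 0 | 12.6 | 24.5 |

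For example, 12 × (90 − 10)/30.4 = 31.6, or 53% of 60, and 2 × 80/30.4 = 5.3, or 9%. With L = 28 the day-90 range is 2 × 62/30.4 = 4.08 to 12 × 62/30.4 = 24.47, or 7% to 41%.

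A direct count with 60 patients enrolled evenly over 3, 6 or 12 months (20, 10 or 5 per month) and L from 10 to 28 leaves 11 to 52 day-90 scores not yet due, or 18% to 87%.

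Both calculations ignore deaths. A patient who has already died has a settled score of 8, so the number truly outstanding would be somewhat lower.

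**4. Which analysis opens the codes.** Two readings fit section 9. If the analysis referred to is the discharge-triggered one, the arms could be revealed up to 90 − L days before the last day-90 score. If it is an analysis after day 90, they would not be. The text does not choose between them, and no day-90 analysis is described.

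**The case against.** The strongest reply is that early unblinding appears nowhere in the documents. Section 9 labels the discharge-time analysis phase 1, and the synopsis and section 4.1 define a second phase at days 60 and 90. It is therefore natural to regard statistical analysis as complete only after phase 2. Comparative data are confined to the DSMB and its statistician, code access is confined to the pharmacist, and neither limit is lifted at phase 1. Section 10.1.5 also promises a charter with firewall procedures. An analysis of group A against group B does not in itself tell a telephone interviewer or a patient the allocation.

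Most of this stands. A reader might infer that discharge of the 60th patient triggers unblinding, but the documents do not say so. What remains is that no text expressly carries the blind through the day-90 assessments or names the assessors and participants who must stay blinded.

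Other stronger readings also fail:
- Section 4.4 does not end the blind at the day-7 blood draw. It lists the double-blind period and the final blood collection as two separate items.
- Scores not yet due are not lost. Sections 4.1 and 4.4 keep follow-up to days 60 and 90, and nothing says day-90 scores would be analyzed from the partial set, so no loss of power can be claimed.
- The patient-reported dyspnea measure is not part of the primary endpoint, and scores 3 to 8 reflect hospital status, respiratory or organ support, or death.
- That the trigger could never be met if the 60th patient died in hospital is an over-literal reading.

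It can also be said that section 4.4 calls 90-day outcomes secondary and that the Schedule of Activities leaves the WHO scale blank at days 60 and 90. This is a separate inconsistency to be settled. It does not remove the synopsis and section 3.1 statements that make those days primary.

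**Conclusion.** The point holds for timing. The single stated trigger disagrees with the synopsis on when phase 1 ends and is not tied to days 28, 60 or 90. Unless the last patient's stay is very long or enrollment of the last patients is long delayed, day-60 and day-90 primary scores will be outstanding when it is met. The day-28 shortfall is conditional: it arises only if the 60th patient leaves before day 28.

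Under the assumed 2 to 12 patients per month, about 5 to 32 of 60 would owe day 90 after a 10-day stay and about 4 to 24 after a 28-day stay. About 1 to 7 would owe day 28 after a 10-day stay, and none after 28 days. The direction follows from the text; the size rests on assumed accrual and stay.

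On blinding, the finding is an omission: the analysis that precedes unblinding is not identified. The existing restrictions lower the risk but give no explicit assurance to day 90.

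**What to change.** Replace the discharge trigger in section 9 with wording such as:

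> Day-28 data are analyzed once every randomized patient has reached day 28, died or withdrawn. The day-60 and day-90 primary comparisons are analyzed once every randomized patient has reached day 90, died or withdrawn.

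Add to Model Set-Up:

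> Treatment codes and comparative results stay sealed from investigators, outcome assessors and participants until the day-90 database is locked. Any day-28 comparison before then is run and held by the DSMB's independent statistician.

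Reconcile this with the statement that no interim analysis is planned, in one of two ways: defer all comparative analysis to day 90, or describe the day-28 analysis as the final analysis of that time point with no effect on trial conduct. Make the phase 1 label match the synopsis.

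The cost is later release of results: 90 − 10 = 80 days after the last discharge for a day-10 discharge, or 62 days for a 28-day stay. No patients or visits are added, and the independent statistician is already in the plan.
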